#### **7.2.9 Cycles 5-12, Day 1 (Day 29 of prior cycle)**

First dose of next cycle may be delayed up to 4 weeks.

- APR-246 (administered Days 1-4)
- Azacitidine (administered Days 1-5)
- Physical exam with Weight; Does not need to be repeated if done within 3 days prior
- Vital signs; Does not need to be repeated if done within 3 days prior
- CBC; Does not need to be repeated if done within 3 days prior

- CMP; Does not need to be repeated if done within 3 days prior
- Adverse events
- Concomitant medications

#### **7.2.10 Cycles 5-12, Days 2, 3, 4, 5**

- APR-246 (administered Days 1-4)
- Azacitidine (administered Days 1-5)
- Additional ECG monitoring in select patients; see Section 6.2
- Adverse events
- Concomitant medications

#### **7.2.11 Cycles 5-12, Day 14**

- CMP
- Adverse events
- Concomitant medications

#### **7.2.12 Cycles 5-12, Day 28**

Every cycle:

- Physical exam with Weight
- Vital signs
- CBC
- CMP
- GVHD evaluation
- Adverse events
- Concomitant medications
- Disease assessment, blood

Additionally, Every 3 cycles/months:

- Disease assessment, bone marrow end of Cycle/Month 6, 9, 12
  - Bone marrow aspirate sample and biopsy core are collected for MRD assessment and correlatives/exploratory (per Section 8.5) when bone marrow is sampled for disease assessment.
- Chimerism, end of Cycle/Month 6, 9, 12

Additionally, Every 6 cycles/months:

- Immune reconstitution, end of Cycle/Month 5, 11

### **7.3 End of Treatment Visit**

Patients discontinuing study early should complete their end of treatment (EOT) visit within 30 days after their last dose. For patients who complete treatment per protocol, EOT is the last day of APR-246 and azacitidine dosing in Cycle 12.

If patients discontinue prior to receiving any APR-246 or azacitidine, the EOT is the date of relapse or Day 100 post-HSCT (the last day of post-transplant window eligibility requirement).

The following should be performed at EOT:

- Disease assessment (blood and bone marrow)
- Vital signs
- CBC
- CMP
- ECGs; see Table 7.
- Pregnancy test (women of child-bearing potential only)
- Adverse events
- Concomitant medications

### **7.4 30 Day Safety Follow-up Visit**

This visit applies only to patients who received any APR-246 or azacitidine. This visit should occur 30 days after the last dose.

- Adverse events
- Concomitant medications

### **7.5 Long-Term Follow-up**

This applies to all patients. Long term follow-up via phone call for survival will occur every 6 months until death or study closure. If GVHD or response assessment is conducted by the site per institutional standard of care, the site should report results to the sponsor until relapse is documented.

## **8.0 STUDY ASSESSMENTS**

### **8.1 Safety Assessments**

#### **8.1.1 Safety Analysis**

Safety data will be tabulated for all patients and include vital signs, laboratory parameters, ECGs and adverse events.

#### **8.1.2 Safety Evaluation**

A safety evaluation will be performed by the Safety Monitoring Committee after the first 6 patients have completed 1 cycle of APR-246 and azacitidine combination therapy. The Committee will decide if it is appropriate to continue at the current dose; or, in the event of the combination is not tolerated (e.g. patients experience dose limiting toxicity) the dose of APR-246 will be reduced for subsequent enrolled patients.

Adverse events and lab values will be reviewed. No formal analysis is planned.

#### **8.1.3 Reporting of Adverse Events**

##### **8.1.3.1 Adverse Events**

An adverse event (AE) is any untoward medical occurrence in a patient or clinical investigation subject administered a pharmaceutical product that does not necessarily have a causal relationship with the treatment. An adverse event can be any unfavorable and unintended sign (including a laboratory finding), symptom or disease temporally associated with the use of a medicinal (investigational) product, whether or not related to the medicinal (investigational) product.

The AE reporting period starts from the day of signing consent. If an AE occurs before the first dose of study drug it will be considered a non-treatment emergent AE. All AEs will be collected for 30 days after the last dose of study drug; see Section 8.1.4 for GVHD reporting.

At each evaluation patients should be interviewed in a non-directed manner to elicit potential adverse reactions from the patient. The occurrence of an adverse event will be based on changes in the patient's physical examination, laboratory results, and/or signs and symptoms.

All adverse events (except grade 1 and 2 laboratory abnormalities that do not require an intervention), regardless of causal relationship, are to be recorded in the case report form and source documentation. The Investigator must determine the intensity of any adverse events according to the NCI Common Terminology Criteria for Adverse Events (CTCAE) Version 5.0 (see [https://ctep.cancer.gov/protocoldevelopment/electronic\\_applications/ctc.htm#ctc\\_50](https://ctep.cancer.gov/protocoldevelopment/electronic_applications/ctc.htm#ctc_50)) and their causal relationship. Those AEs not covered by these criteria will be graded as follows:

1. Mild: Discomfort noticed, but no disruption of normal daily activity. Prescription drug not ordinarily needed for relief of symptom but may be given because of personality of patient.
2. Moderate: Discomfort sufficient to reduce or affect normal daily activity. Patient is able to continue in study; treatment for symptom may be needed.
3. Severe: Incapacitating, severe discomfort with inability to work or to perform normal daily activity. Severity may cause cessation of treatment with test drug; treatment for symptom may be given and/or patient hospitalized.
4. Life-Threatening: Symptom(s) place the patient at immediate risk of death from the reaction as it occurred; it does not include a reaction that, had it occurred in a more serious form, might have caused death.
5. Fatal: Event caused the death of the patient.

Adverse events will be followed until resolution or stabilization while the patient remains on-study. Once the patient is removed from study, events thought to be related to the study medication will be followed until resolution or stabilization, unless, in the Investigator's opinion the event is unlikely to resolve due to the patient's underlying disease, or until the patient starts a new treatment regimen or the patient is lost to follow-up.

### **8.1.3.2 Attribution Definitions**

An adverse event is considered to be associated with the use of the Investigational agent if the attribution is determined as possible, probable or definite. Attribution of AEs will be recorded in the CRF as:

- Unrelated: The AE is clearly NOT related to the study treatment.
- Unlikely: The AE is doubtfully related to the study treatment.
- Possible: The AE may be related to the study treatment.
- Probable: The AE is likely related to the study treatment.
- Definite: The AE is clearly related to the study treatment.

### **8.1.3.3 Definition of an Unexpected Adverse Event**

An unexpected adverse event is defined as any adverse drug experience, the specificity or severity of which is not consistent with the current Investigator Brochure; or, if an Investigator Brochure is not available, the specificity or severity of which is not consistent with the risk information described in this protocol or in the regulatory agency study authorization application.

Unexpected, as used in this definition, refers to an adverse drug experience that has not been previously observed (e.g., included in the Investigator Brochure) rather than from the perspective of such experience not being anticipated from the pharmacological properties of the pharmaceutical product.

### **8.1.4 GVHD Adverse Event Reporting**

All occurrences of GVHD will be reported as Adverse Events (or SAEs), regardless of their start date in relation to study drug. Acute GVHD will be followed until resolution, or until further improvement is no longer expected. Chronic GVHD events will be collected for 30 days after the last dose of study drug.

GVHD evaluation and grading will be performed per Harris 2016 (APPENDIX C) and Jagasia 2015 (APPENDIX D).

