### **Safety Analyses:**

Safety data including adverse events, vital signs, laboratory data, ECG, physical exam will be tabulated for the Safety Evaluable population. Adverse events will be tabulated by body system, preferred term, severity, and relationship. The tabulation of laboratory parameters will include the normal ranges for each parameter. Each value will be classified as falling above, below, or within the normal range. Laboratory parameters will also be tabulated by maximum NCI-CTCAE v5 severity grade. Incidence and grade of acute and chronic GVHD at 1-year and cumulative will be summarized by number (%) of subjects for each dose level and overall.

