#### **3.2 Secondary Objectives**

1. To assess the overall survival (OS).
2. To assess non-relapse mortality (NRM).
3. To assess time to progression (TTP).
4. To evaluate cumulative incidence of Grades II-IV and III-IV acute graft versus host disease (GVHD).
5. To evaluate 12-month cumulative incidence of mild, moderate, and severe GVHD.
6. To describe event-free survival (EFS).

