#### **8.1.4.3 Reporting of Serious Adverse Events**

Adverse events classified as serious require expeditious handling and reporting to [REDACTED] to comply with regulatory requirements.

For any serious adverse event (SAE) that occurs from APR-246 consent up to 30 days after the last study drug administration, regardless of any opinion as to the relationship of the SAE to the study drug; or if any SAE that the Investigator feels is related to the study drug occurs later than 30 days after the last study drug administration, the [REDACTED]

[REDACTED]  
[REDACTED]  
[REDACTED]  
[REDACTED]  
[REDACTED]

All SAEs require that a Serious Adverse Event Report Form be completed and sent as a PDF via email (preferred method) or faxed to [REDACTED] at the address below within 24 hours of becoming aware of the event.

In the USA, SAEs will be reported to: [REDACTED]

[REDACTED]  
[REDACTED]  
[REDACTED]

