### 9.1 Safety

Safety data including adverse events, vital signs, laboratory data, ECG, physical exam will be tabulated for the Safety Evaluable population which is all subjects who are registered on the study and received any dose of APR-246 or azacitidine. Adverse events will be tabulated by body system, preferred term, severity, and relationship to study drugs. The tabulation of laboratory parameters will include the normal ranges for each parameter. Each value will be classified as falling above, below, or within the normal range. Laboratory parameters will also be tabulated by maximum NCI-CTCAE v5 severity grade. Incidence and grade of acute and chronic GVHD at 1-year and cumulative will be summarized by number (%) of subjects for each dose level and overall.

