**Table 11: Cycle 5-12 (Treatment Period), EOT, 30 day Safety FUV, LTFU**

Day	APR-246/AZA Treatment Cycles 5 - 12					EOT (5)	Follow-up safety visit	Long Term Follow-up (6)
	1 (D29 prior cycle)	2, 3, 4	5	14	28			
Window	+28			+/- 3	+/- 3 *			
APR-246	X	X						
Azacitidine	X	X	X					
Physical Exam with Weight	X (3)				X			
Vital Signs	X (3)				X	X		
CBC	X (3)				X	X		
CMP	X (3)			X	X	X		
Cardiac function (ECG)	X (4)	X (4)				X		
Pregnancy Test (1)						X		
Disease Assessment					X (8)	X	X (6)	
BM/BMA for Correlatives/exploratory (2)					C 6, 9, 12 (2)			
GVHD monitoring					X		X (6)	
Blood sample (chimerism) (7)					C 6, 9, 12			
Blood sample for flow (immune reconstitution)					C 5, 11			
Adverse Events	X	X	X	X	X	X	X	
Concomitant Medications	X	X	X	X	X	X	X	
Survival								every 6 months

(1) Pregnancy test applies to women of child-bearing potential only.

(2) Bone marrow aspirate sample and biopsy core are collected for correlatives/exploratory (per Section 8.5) when bone marrow is sampled for disease assessment.

(3) Do not need to repeat if done within 3 days prior to dosing.

(4) After Cycle 4, perform additional ECG monitoring in select patients; see Section 6.2.

(5) EOT: see Section 7.3.

(6) LTFU applies to all patients. LTFU via phone call for survival will occur every 6 months until death or study closure. If GVHD or response assessment is conducted by the site per institutional standard of care, the site should report results to the sponsor until relapse is documented.

(7) CD3/CD33 in the blood should be done every 3 months same time marrows for disease assessment are being done. Additionally, whole bone marrow chimerism should be done from the marrow every 3 months collected at same time disease assessment labs are done

(8) Disease assessment by blood test must be done after every cycle. Response assessment based on CBC may utilize the most recently

available bone marrow results. Disease assessment by bone marrow is done C3.

\* Up to 14 day window is permitted for disease assessments.

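### The 12-month chronic GVHD incidence is a percentage of all treated patients, but required collection stops 30 days after the last dose, so it is a lower bound

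*Combined protocol and SAP*

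**What the plan says.** - **Objective.** Section 3.2 lists "To evaluate 12-month cumulative incidence of mild, moderate, and severe GVHD". Mild, moderate and severe are the chronic GVHD categories of Appendix D. Acute GVHD has its own objective, by grades II-IV and III-IV.
- **Summary.** Section 9.1 states "Incidence and grade of acute and chronic GVHD at 1-year and cumulative will be summarized by number (%) of subjects". The synopsis (Safety Analyses) matches: "by number (%) of subjects for each dose level and overall". The paragraph concerns the Safety Evaluable population, "all subjects who are registered on the study and received any dose of APR-246 or azacitidine".
- **Required collection.** Section 8.1.4: "Chronic GVHD events will be collected for 30 days after the last dose of study drug". The same section opens by asking for every GVHD occurrence whatever its start date relative to study drug. It sets no 30-day end for acute GVHD.
- **Later reporting.** Section 7.5: "If GVHD or response assessment is conducted by the site per institutional standard of care, the site should report results to the sponsor". Table 11, footnote 6, gives the end point: "the site should report results to the sponsor until relapse is documented". The only required long-term contact is a survival phone call every 6 months. The other late route is Section 8.1.4.3, which covers "any SAE that the Investigator feels is related to the study drug occurs later than 30 days after the last study drug administration".
- **Not stated.** The plan gives no time origin, estimator, censoring rule or competing event for the GVHD incidence objectives. Sections 9.3.3 and 9.3.4 do name competing events for non-relapse mortality and time to progression.

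**The concern.** A simple percentage equals a 12-month cumulative incidence only if each patient's GVHD status is known to month 12, or to death if earlier. Here the denominator is everyone treated, while required observation ends with treatment plus 30 days. Section 4.5 says early stoppers are followed for relapse and survival; it does not name GVHD. Chronic GVHD that appears after the 30-day limit and is not reported is therefore scored as no GVHD.

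At stake is the accuracy of a harm estimate in a post-transplant setting. It would be labelled a 12-month cumulative incidence but would depend on how many late cases sites report. A confidence interval around the percentage does not show this shortfall.

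**Working it through.** The documents give no GVHD rate to reproduce, so the check has two parts: the calendar and an illustration.

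**Calendar** (28-day cycles, last azacitidine dose on Day 5, no delays; first dose is day 1)
- Last dose Cycle 3 Day 5: 1 + 2×28 + 4 = day 61. Required collection ends on day 61 + 30 = 91. With first dose on HSCT Day 30 or 100, that is HSCT day 120 or 190.
- Last dose Cycle 12 Day 5: 1 + 11×28 + 4 = day 313. Collection ends on day 343, about 3 weeks short of 12 months from first dose. Counted from HSCT it is day 372 or later, so completers are covered.

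The gap therefore lies mainly with patients who stop early.

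**Illustration** (first-dose origin, constant hazards per month)
- Relapse or death: 50% at 1 year, the alternative in Section 9.2, so λ = ln 2/12 = 0.0578.
- True 12-month chronic GVHD incidence C: 30% or 40% (assumed). Solving C = h/(h+λ) × (1 − exp(−12(h+λ))) gives h = 0.0431 or 0.0632.
- Stopping for other reasons: s = 20%, 30% or 50% by month 12 (assumed), so μ = −ln(1−s)/12 = 0.0186, 0.0297 or 0.0578. This is added to relapse or death, so the total relapsed, dead or off treatment is 1 − 0.5(1−s) = 60%, 65% or 75%.
- Share captured = ∫₀¹² h·exp(−(h+λ)t)·P(stop > t−1) dt, where the one-month lag stands for the 30 days.

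Example, C = 30%, s = 30%:
- Month 0-1: (0.0431/0.1009)(1 − e^−0.1009) = 0.041.
- Months 1-12: (0.0431·e^0.0297/0.1306)(e^−0.1306 − e^−1.567) = 0.2275.
- Sum 0.2685; loss 31 × (0.30 − 0.2685) = 0.98 patients.

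| True | Other stopping (total) | Captured | Lost of 31: none reported late | Half | 80% |
|---|---|---|---|---|---|
| 30% | 20% (60%) | 28.0% | 0.63 | 0.32 | 0.13 |
| 30% | 30% (65%) | 26.8% | 0.98 | 0.49 | 0.20 |
| 30% | 50% (75%) | 24.4% | 1.74 | 0.87 | 0.35 |
| 40% | 20% (60%) | 37.4% | 0.80 | 0.40 | 0.16 |
| 40% | 30% (65%) | 36.0% | 1.23 | 0.62 | 0.25 |
| 40% | 50% (75%) | 32.9% | 2.20 | 1.10 | 0.44 |

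With full reporting the loss is zero. Ending completers' collection at day 343 raises the no-late-reporting range for 30-50% stopping from 0.98-2.20 to 1.20-2.39.

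**Sensitivity to relapse.** The table ends GVHD risk at relapse. If only death competes (0-30% at 12 months, assumed), chronic GVHD after relapse still counts. With 30-50% stopping in all, a true 30% then shows as 22-26%, which is 6.9-7.9 patients against 9.3.

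**Scale.** The 95% half-width is 1.96·√(p(1−p)/31) = 0.161 at 30% and 0.172 at 40%, or 5.0 and 5.3 patients.

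**The case against.** The strongest reply is that Section 7.5 already covers most of the gap. Long-term follow-up applies to all patients, and sites are asked to report GVHD they assess until relapse. The cases lost in the table all precede relapse, so each falls within that request, and the 1-2 patient figure needs sites to report nothing under it. This stands as a limit on size: with 80% reported, the loss is 0.2-0.4 patients. It does not remove the point, because the request depends on local practice, ends at relapse, and sits beside a 30-day limit in Section 8.1.4 that a site could take as the rule.

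Two further replies stand. Severe chronic GVHD on treatment is itself listed in Section 4.5 as ending treatment, so those cases fall inside the window. With complete ascertainment, number (%) is a valid cumulative incidence; deaths in the denominator are not an error.

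A reader might infer more than the documents support:
- **That all chronic GVHD after the 30 days is discarded.** Sections 7.5 and 8.1.4.3 leave routes open, and the opening of 8.1.4 points towards full reporting.
- **That acute GVHD is cut off in the same way.** Section 8.1.4 sets no such limit for it.
- **That 30-50% early stopping is the total off treatment.** In the table it comes on top of 50% relapse or death. If relapse and death were the only reasons treatment ended, the table's loss would be zero.

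**Conclusion.** The point holds for chronic GVHD. As written, the plan counts patients without required observation as non-cases, so the 12-month percentage is a lower bound.

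The likely shortfall is small: about 1-2 of 31 patients if nothing is reported late and 65-75% are relapsed, dead or off treatment by month 12; 0.6-0.8 at 60%; and less in proportion to late reporting. That is below the sampling half-width of about 5 patients, but it is systematic and always in one direction. Apart from the 50% one-year relapse-free survival, the rates are assumptions, and the result varies with the time origin and the handling of relapse, neither of which the plan states for GVHD.

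The endpoint is descriptive, with no control arm and no GVHD decision rule, and the primary analysis is not affected. The change is worth making because it is cheap and alters a reported secondary result.

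**What to change.** 1. **Data.** Reconcile Section 8.1.4 with Section 7.5 and Table 11 footnote 6, so that chronic GVHD status already in site records is reported to 12 months from a stated origin for every treated patient, whatever the treatment or relapse status. No added visits or tests are needed.
2. **Analysis.** In Section 9.1 and the synopsis, estimate the 12-month chronic GVHD cumulative incidence by Aalen-Johansen. Take death as a competing event and state how relapse is handled. End observation at the last documented GVHD assessment, negative ones included, under one rule for cases and non-cases. Counting late cases while censoring non-cases at the 30-day limit would overshoot (32-33% for a true 30% with half of late cases captured, under the same kind of assumptions). Keep number (%) as a supplementary table with a note on incomplete follow-up.
3. **Origin.** Choose it with regard to the registration origin used for relapse-free, overall and event-free survival. First dose is one option, since only treated patients are analysed.

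The cost is wording in four places, one analysis program and some data entry from existing records. Some late cases may not be scorable for severity (Appendix D uses FEV1 for the lung) and would be recorded as present, severity unknown. Aalen-Johansen assumes that censoring is non-informative, so step 2 does not replace step 1.

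Separately, Section 4.5 lists grade 3-4 acute and severe chronic GVHD among the reasons treatment ends, while Section 6.3.1 asks for every effort to continue study drug when GVHD appears or worsens. These passages must be reconciled; they also bear on whether stopping is informative.

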#### **8.1.4.1 Serious Adverse Event (SAE)**

A serious adverse event is defined as any untoward medical occurrence that at any dose:

1. Results in death,
2. Is life-threatening (i.e., the patient was at risk of death at the time of the event. It does not refer to an event which hypothetically might have caused death if it was more severe),

3. Requires in-patient hospitalization or prolongation of existing hospitalization excluding that for pain management, disease staging/re-staging procedures, or catheter placement unless associated with other serious events,
4. Results in persistent or significant disability/incapacity, or
5. Is a congenital anomaly/birth defect.

Important medical events that may not result in death, be life-threatening, or require hospitalization may be considered serious adverse drug events when, based on appropriate medical judgment, they may jeopardize the patient or subject and may require medical or surgical intervention to prevent one of the outcomes listed above.

#### **8.1.4.2 Pregnancy**

Any pregnancy diagnosed during the study, or that occurs within 30 days after stopping study medication, must be reported immediately to the Investigator. Pregnancy, in and of itself, is not regarded as an adverse event, unless there is suspicion that study medication may have interfered with the effectiveness of a contraceptive medication. If the patient becomes pregnant while on-study, the study drug should be immediately discontinued. Pregnancy information about a female patient or a female partner of a male patient should be reported immediately from the time the Investigator first becomes aware of a pregnancy or its outcome. This will be performed by the Investigator completing a Pregnancy Form and emailing it or faxing it to the [REDACTED]  
[REDACTED]

Any pregnancy complication, spontaneous abortion, elective termination of a pregnancy for medical reasons, outcome of stillbirth, congenital anomaly/birth defect, or serious adverse event in the mother will be recorded as an SAE and will be reported as described in Section 8.1.4.3.

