#### **4.4 End of Study**

The end of the study is defined as the date of the last visit of the last patient undergoing the trial.

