### 5.1 Pre-Screening

#### 5.1.1 Inclusion Criteria

These observations will be done  $\leq$  28 days prior to beginning conditioning chemotherapy in anticipation for allograft infusion.

1. Documentation of a *TP53* gene mutation (which is not benign or likely benign) by NGS based on local evaluation with study eligibility confirmed centrally.
2. Must provide a pre-HSCT bone marrow biopsy.
3. Age  $\geq$ 18 years at the time of signing the informed consent form
4. Institutional Review Board/Independent Ethics Committee (IRB/IEC) approved written informed consent and privacy language as per national regulations (e.g., Health Insurance Portability and Accountability Act Authorization (HIPAA) for US sites) obtained from the participant or legally authorized representative prior to any study-related procedures (including withdrawal of prohibited medication, if applicable).
5. Patient has confirmed, morphologically documented MDS or AML by WHO criteria.
6. Patient is considered a suitable candidate for HSCT and has an acceptable source of allogeneic donor hematopoietic stem cells, as defined per institutional practice (allogeneic HSCT for any donor source [matched sibling, unrelated donor (URD), mismatched URD, related haploidentical] and any graft source [BM, PB], and any non-study conditioning [myeloablative conditioning (MAC), reduced intensity conditioning (RIC), or non-myeloablative conditioning (NMA)] will be permitted). Additionally, any standard (non-study) GVHD prophylaxis regimen will be permitted.
7. Females must either:
  - a. Be of non-childbearing potential
    - i. postmenopausal (defined as at least 1 year without menses) prior to screening, or
    - ii. documented as surgically sterilized at least 1 month prior to the screening visit

- b. Or, if of childbearing potential,
  - i. Agree not to try to become pregnant during the study and for 6 months after the final study drug administration
  - ii. And have a negative serum pregnancy test at screening
  - iii. And, if heterosexually active, agree to consistently use highly effective contraception per locally accepted standards in addition to a barrier method starting at screening and throughout the study period and for 6 months after final study drug administration.
8. Females must agree not to breastfeed or donate ova throughout the study drug treatment period and for 6 months after the final study drug administration.

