9. Males (even if surgically sterilized), and their partners who are women of childbearing potential must be using highly effective contraception in addition to a barrier method throughout the study drug treatment period and for 127 days after the final study drug administration.
10. Males must not donate sperm throughout the study drug treatment period and for 127 days after the final study drug administration.

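### The stated post-dose limb of the pregnancy reporting window (30 days) is shorter than the protocol's own precaution periods (6 months for women, 127 days for men), and nothing scheduled after end of treatment asks about pregnancy

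*Combined protocol and SAP*

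**What the plan says.** Section 8.1.4.2 opens with the window: "Any pregnancy diagnosed during the study, or that occurs within 30 days after stopping study medication, must be reported immediately to the Investigator". The sentence is passive and does not say who must report. *During the study* is not defined there.

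The same paragraph then deals with onward reporting, without an end date and with partners included: "Pregnancy information about a female patient or a female partner of a male patient should be reported immediately". The trigger is awareness; the information "should be reported immediately from the time the Investigator first becomes aware of a pregnancy or its outcome". Section 8.1.4.3 also extends serious adverse event (SAE) reporting to "any SAE that the Investigator feels is related to the study drug occurs later than 30 days after the last study drug administration".

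The precaution periods are in the eligibility criteria. Section 5.1.1 item 7 has women of childbearing potential "Agree not to try to become pregnant during the study and for 6 months after the final study drug administration", and Section 5.2.1 repeats the 6 months. For men, Section 5.1.1 items 9 and 10 continue contraception and the ban on sperm donation "for 127 days after the final study drug administration".

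Pregnancy tests are listed at pre-screening, at post-transplant screening and at EOT (Sections 7.1.1, 7.1.3 and 7.3; Tables 10 and 11), and only for women of childbearing potential. For patients who complete treatment, "EOT is the last day of APR-246 and azacitidine dosing in Cycle 12"; early discontinuers have the visit within 30 days of their last dose. The 30-day safety visit (Section 7.4) lists adverse events and concomitant medications. Long-term follow-up (Section 7.5) is a 6-monthly telephone call for survival, with GVHD or response results added if the site happens to assess them.

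**The concern.** The protocol treats a pregnancy as a matter for caution until 6 months after the last dose in a female patient and until 127 days in the partner of a male patient. The only post-dose limit that Section 8.1.4.2 puts on telling the Investigator is 30 days. A stated rule is thus shorter than the risk period that the same protocol recognises.

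What is at stake is capture of pregnancies conceived after day 30 but inside the precaution period. Once the Investigator knows of one, it is reportable. The weak link is how the Investigator comes to know. Section 8.1.4.2 says that pregnancy alone is not an adverse event, so the adverse-event questioning at the 30-day visit does not by definition bring it out. No scheduled item asks male patients about their partners at any time.

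**Working it through.** The plan gives no figure to reproduce here. The check compares the windows, then reads the schedule.

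**Inputs**
- Post-dose limb of the reporting window: 30 days (Section 8.1.4.2).
- Precaution period, women: 6 months (Sections 5.1.1 and 5.2.1). Assumption: 6 months = 183 days, range 181 to 184.
- Precaution period, men: 127 days (Section 5.1.1 items 9 and 10).

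**Step 1. Narrow reading: *during the study* means the treatment period.** Days outside the window = precaution period minus 30.
- Women: 183 − 30 = 153 days (181 − 30 = 151 to 184 − 30 = 154). As a share of the period, 153/183 = 84%.
- Partners of men: 127 − 30 = 97 days. As a share, 97/127 = 76%.

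**Step 2. Broad reading: *during the study* runs through long-term follow-up.** Section 4.4 supports this: "The end of the study is defined as the date of the last visit of the last patient undergoing the trial". Section 7.5 keeps all patients in follow-up until death or study closure. While the study is open and the patient is in it, days outside the window = 0. For a patient who leaves, or whose study closes, soon after the last dose, only the 30-day limb remains, and the gap grows from 0 towards the values in Step 1. I find no stated minimum interval between a patient's last dose and study closure, so this case cannot be ruled out.

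**Step 3. Scheduled prompts after the last dose.**
- Last scheduled pregnancy test: day 0 after the last dose for patients who complete Cycle 12; by day 30 for early discontinuers.
- Pregnancy tests or questions scheduled after EOT: 0 (Sections 7.4 and 7.5, Table 11).

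**Step 4. Would a question at existing contacts cover the period?** Section 7.5 does not say from when the 6 months are counted. Assuming they run from EOT, the first call falls at about day 183 after the last dose (completers) to day 30 + 183 = 213 (early discontinuers who have EOT on day 30). One question there looks back over the full 127 days and, to within the calendar assumption, the full 6 months.

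**The case against.** The best case for the present text has four parts.

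*The broad reading may be the right one.* Elsewhere the protocol uses a separate term for the drug treatment period, and Section 8.1.4.2 does not use it. Nor does the broad reading make the 30-day limb redundant: the first limb concerns when a pregnancy is diagnosed and the second when it occurs, so a pregnancy that occurs by day 30 but is diagnosed after closure is caught only by the second. This stands, and it is why the 153 and 97 days must not be quoted without the 0 beside them. Against it, Section 5.1.1 item 7 sets *the study* apart from the 6 months after the last dose, so the question is not settled. Even on the broad reading the 30-day limb alone governs patients who leave early or whose study closes.

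*Later pregnancies are already reportable.* A reader might infer that a pregnancy after day 30 need not be reported at all. The documents do not support that. Onward reporting runs from awareness with no end date and covers partners, listed complications and outcomes are recorded as SAEs, and related SAEs after 30 days are covered.

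*The text does not say that a patient's duty ends at day 30.* A reader might infer this too, but no reporter is named. The consent pages and the Pregnancy Form are not available for this review, so what patients are told, and for how long, is unknown. That objection stands in full.

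*Men are bound for 127 days.* Section 5.2.1 items 8 and 9 and the matching synopsis items omit the 127 days, and a reader might infer that treated men have no precautions after the last dose. Section 5.0 requires the criteria of both 5.1 and 5.2 to be met, so Section 5.1.1 already binds them. The omission adds no weight.

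What is left is that detection after EOT is passive. Unscheduled visits are allowed (Section 7.0), but nothing in the schedule prompts the question.

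**Conclusion.** The point holds as a wording mismatch with a modest consequence. The stated post-dose limb is 30 days against precaution periods of 6 months and 127 days; that much is plain on the page. The size of the gap depends on an undefined phrase: 0 days for a patient still in an open study on the broad reading, up to about 153 days (women, with 6 months taken as 183 days) or 97 days (partners of men) on the narrow one. No pregnancy test or question is scheduled after EOT in the visible schedule.

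The documents give no expected number of pregnancies, and the trial has about 31 patients, so few events are likely to be at issue. The matter concerns safety capture only and has no bearing on sample size, power or the relapse-free survival analysis. It is an inexpensive improvement and should not be presented as a failure of pregnancy reporting.

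**What to change.** - In Section 8.1.4.2, replace the 30-day limit with 6 months after the last dose for female patients and 127 days after the last dose for female partners of male patients. The meaning of *during the study* then no longer matters for the risk period.
- Add one question, on pregnancy in the patient or a partner, to the 30-day safety visit (Section 7.4) and to the first 6-month follow-up call (Section 7.5), and show both in Table 11.
- Optional tidy-up: add the 127 days to Section 5.2.1 items 8 and 9 and the matching synopsis items.

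The cost is minor protocol wording, with consent wording if it needs to match, one question at two contacts that already exist, and rare extra reports.
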